#### 9.7.2.4 Analysis of the Primary and Secondary Endpoints

Analysis of Primary Objective:

Congenital anomalies will be summarised and descriptive statistics will be presented.

Congenital anomalies will be defined according to ICD10-BPA codes (codes included in Appendix E: EUROCAT Subgroups of Congenital Anomalies).

Analyses of Secondary Objectives:

Secondary objective outcome measures will be summarised and descriptive statistics will be presented.

Due to potentially insufficient data and consequent lack of statistical power, it is unlikely that comparisons between the 2 groups will provide meaningful results, hence, no formal comparison of exposed/unexposed subjects is planned.

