#### 9.3 Outcomes - Variables

Information available for each subject on all variables will be reported by study site staff in the study-specific database held by the sponsor. The original data source will be patient (maternal – infant) records, from routine follow-up of subjects:

- Maternal Data:
  - Demographics:
    - Country of residence
    - Age (at start of pregnancy, categorized into  $\leq$  19, 20-24, 25-29, 30-34, 35-39, 40-44,  $\geq$  45 year age categories)
    - Education (highest level)
    - Occupation
    - Height and weight (to calculate body mass index, categorised into < 20, 20-24, 25-29, ≥ 30 kg/m^2 body mass index categories)
  - Current pregnancy history:
    - Date of last menstrual period
    - Estimated date of delivery
    - Number of fetuses
    - Treatment for infertility

CONFIDENTIAL

- Medical history:
  - FH diagnosis status and method of diagnosis
  - Presence of significant comorbid conditions (hypertension, diabetes mellitus, epilepsy, other)
  - o Family history of congenital disorders
- Obstetric history:
  - Number of previous pregnancies and outcome
  - Previous maternal pregnancy complications
  - Previous fetal/neonatal abnormalities
  - History of subfertility
- Medications (product, dose, dose dates) taken within 3 months prior to or during pregnancy (excluding medication routinely administered during labour/delivery) and/or breast-feeding
- Lipid levels (triglycerides, total cholesterol, LDL-C, HDL-C)
- Congenital anomaly including congenital abnormality or malformation as defined by European Surveillance of Congenital Anomalies (EUROCAT) (See Appendix E for full list)
- Complications of pregnancy:
  - Pre-eclampsia
  - Gestational diabetes
- Outcomes of pregnancy: (See Appendix F for further definition):
  - Live birth (with / without congenital anomaly)
  - Neonatal death (with / without congenital anomaly)
  - Stillbirth (with / without congenital anomaly)
  - Elective termination (with / without congenital anomaly)
  - Miscarriage (with / without congenital anomaly)
  - Spontaneous abortion
  - Ectopic pregnancy
  - Molar pregnancy
- Mode of delivery:
  - Normal vaginal delivery
  - Operative vaginal delivery
  - Vaginal breech delivery
  - Caesarean section
- Complications of delivery:
  - Abnormal Cord gas
  - Fetal heart rate abnormalities
  - Abnormal amniotic fluid

- Blood transfusion resulting from post-partum haemorrhage;
- Thromboembolism
- Infant Data:
  - Infant status at delivery:

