#### 9.3.2 Outcome Assessment

Outcome Measures:

- The primary outcome measure is congenital anomaly. Any incidence of congenital anomaly will be diagnosed and classified by the study site Investigator, or by the subject's treating physician (eg, an obstetrician, paediatrician, neonatologist) if this is not the Investigator, and reported on the study-specific eCRF. Supporting documentation will be requested to enable independent adjudication of the diagnosis, by an external expert not participating as a study investigator. Where supporting documentation is not held at the same clinic/hospital/institution as the study site, contracts will be executed to allow sharing of medical records, as necessary.
- Secondary outcome measures include:
  - Pregnancy outcomes (live birth(s), stillbirth, spontaneous loss, elective termination, ectopic pregnancy, complications of pregnancy (eg, pre-eclampsia, gestational diabetes)
  - Delivery outcomes (mode of delivery; complications including requirement for blood transfusion, thromboembolism, fetal distress, amniotic fluid abnormality)
  - Infant status at delivery: gender; gestational age; Apgar score; birth weight
  - Infant outcomes at 6 and 12 months post-delivery (including growth, hospitalisation, chronic medication)

The secondary outcome measures will be reported on the study-specific eCRF, from information entered into the subject's notes as part of routine follow-up. Where supporting documentation is not held at the same clinic/hospital/institution as the study site, contracts will be executed to allow sharing of medical records, as necessary.

Adverse outcomes requiring a clinical diagnosis of congenital anomaly will be subject to the same independent adjudication as the primary outcome.

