## Appendix D. Additional Safety Reporting Information

Adverse Event Severity Scoring System

Grade	Amgen Standard Adverse Event Severity Scoring System
1	MILD: Aware of sign or symptom, but easily tolerated
2	MODERATE: Discomfort enough to cause interference with usual activity
3	SEVERE: Incapacitating with inability to work or do usual activity

EUROCAT Subgroups	ICD10-BPA	ICD9-BPA	Comments	Excluded	Excluded	Subgroup
				minor	minor	binary
				anomalies	anomalies	variable
				post-2005	pre-2005	number (al)
All anomalies *	Q-chapter,	74, 75,		Exclude all	Exclude all	al1
	D215, D821,	27910,		minor	minor	
	D1810 ° , P350,	2281^,		anomalies as	anomalies as	
	P351, P371	76076,		specified in	specified in	
		76280, 7710,		Guide 1.4,	Guide 1.2	
		7711, 77121		section 3.2	(ICD9 and ICD10)	
Nervous system	Q00, Q01,	740, 741,		Q0461, Q0782	100107	al2
	Q02, Q03,	742		. , .		
	Q04, Q05,					
	Q06, Q07					
Neural Tube Defects	Q00, Q01,	740, 741,				al3
An an an a ball an and	Q05	7420				-14
Anencephalus and similar	Q00	740				al4
Encephalocele	Q01	7420	Exclude if associated			al5
			with anencephalus			
			subgroup			
Spina Bifida	Q05	741	Exclude if associated			al6
			with anencephalus or			
			encephalocele			
		7423	subgroups			
Hydrocephalus	Q03	7423	Exclude			al7
			hydranencephaly			
			74232. Exclude			
			association with NTD			
Microcephaly	Q02	7421	subgroup Exclude association			al8
wierocephary	0,02	/421	with NTD subgroup			810
Arhinencephaly /	Q041, Q042	74226				al9
holoprosencephaly						
Eye	Q10-Q15	743		Q101-Q103, Q105, Q135	74365	al10
Anophthalmos /	Q110, Q111,	7430, 7431				al11
microphthalmos	Q112					
Anophthalmos	Q110, Q111	7430				al12
Congenital cataract	Q120	74332				al13
Congenital glaucoma	Q150	74320				al14
Ear, face and neck	Q16, Q17,	744		Q170-Q175,	74411, 74412,	al15
	Q18			Q179, Q180-	7443, 74491	
				Q182, Q184-		
				Q187, Q1880,		
				Q189		

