equinovarus	0.000	75.430				-167
Hip dislocation and / or dyspasia	Q650-Q652, Q6580,	75430				al67
or dyspasia						
Polydactyly	Q6581 Q69	7550				al68
Syndactyly	Q70	7551				al69
Other anomalies /	0/0	7551				alog
syndromes						
Skeletal dysplasias	Q7402, Q77,	No code				al104
okeletal uyspiasias	Q7800,	No code				a1104
	Q782-Q788,					
Craniosynostosis	Q750	75600				al75
Congenital	Q7980	76280				al76
constriction bands	0.000	/0200				
/ amniotic band						
Situs inversus	Q893	7593				al79
Conjoined twins	Q894	7594				al80
Congenital skin	Q80-Q82	7571, 7573		Q825, Q8280	Q825, Q8280,	al81
disorders					Q8281,	
					75731, 75738	
VATER/VACTERL	Q8726	759895				al112
Vascular disruption	Q0435,	No code				al113
anomalies	Q411, Q412,					
	Q418, Q710,					
	Q712, Q713,					
	Q720, Q722,					
	Q723, Q730,					
	Q793, Q795,					
	Q7980,					
	Q7982,					
	Q8706					
Laterality anomalies	Q206, Q240,	No code				al114
	Q3381,					
-	Q890, Q893	No				-100
Teratogenic	Q86, P350,	No code				al82
syndromes with	P351, P371					
malformations Fetal alcohol	0050	76076				-102
Fetal alcohol syndrome	Q860	76076				al83
	Q8680	No codo				al84
Valproate syndrome Maternal infections	Q8680 P350, P351,	No code 7710, 7711,				al84 al86
resulting in	P350, P351, P371	7710, 7711,				8100
malformations						
manormations		l	1		L	

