		Exposed but stopped prior			Exposed at conception and during 1 st trimester	Exposed	Exposure during breastfeeding	
	Unexposed (N = x)	to conception (N = x)	trimester (N = x)	trimesters (N = x)	trimesters (N = x)	pregnancy (N = x)	only (N = x)	breastfeeding (N = x)
	(N – X) n (%)	(N – X) n (%)	(N – X) n (%)	(N – X) n (%)	(N – X) n (%)	(N – X) n (%)	(N – X) n (%)	(N – X) n (%)
Pregnancies enrolled pre-partum								
All outcomes	x (x.x)	x (x.x)	x (x.x)	x (x.x)	x (x.x)	x (x.x)	x (x.x)	x (x.x)
Live birth without congenital anomaly	x (x.x)	x (x.x)	x (x.x)	x (x.x)	x (x.x)	x (x.x)	x (x.x)	x (x.x)
Live birth with congenital anomaly	x (x.x)	x (x.x)	x (x.x)	x (x.x)	x (x.x)	x (x.x)	x (x.x)	x (x.x)
Neonatal death without congenital anomaly	x (x.x)	x (x.x)	x (x.x)	x (x.x)	x (x.x)	x (x.x)	x (x.x)	x (x.x)
Neonatal death with congenital anomaly	x (x.x)	x (x.x)	x (x.x)	x (x.x)	x (x.x)	x (x.x)	x (x.x)	x (x.x)
Stillbirth without congenital anomaly	x (x.x)	x (x.x)	x (x.x)	x (x.x)	x (x.x)	x (x.x)	x (x.x)	x (x.x)
Stillbirth with congenital anomaly	x (x.x)	x (x.x)	x (x.x)	x (x.x)	x (x.x)	x (x.x)	x (x.x)	x (x.x)
Miscarriage without congenital anomaly	x (x.x)	x (x.x)	x (x.x)	x (x.x)	x (x.x)	x (x.x)	x (x.x)	x (x.x)
Miscarriage with congenital anomaly	x (x.x)	x (x.x)	x (x.x)	x (x.x)	x (x.x)	x (x.x)	x (x.x)	x (x.x)
Termination of pregnancy without congenital anomaly	x (x.x)	x (x.x)	x (x.x)	x (x.x)	x (x.x)	x (x.x)	x (x.x)	x (x.x)
Termination of pregnancy with congenital anomaly	x (x.x)	x (x.x)	x (x.x)	x (x.x)	x (x.x)	x (x.x)	x (x.x)	x (x.x)
Ectopic pregnancy	x (x.x)	x (x.x)	x (x.x)	x (x.x)	x (x.x)	x (x.x)	x (x.x)	x (x.x)
Molar pregnancy	x (x.x)	x (x.x)	x (x.x)	x (x.x)	x (x.x)	x (x.x)	x (x.x)	x (x.x)
Pregnancy continuing at time of data cut-off	x (x.x)	x (x.x)	x (x.x)	x (x.x)	x (x.x)	x (x.x)	x (x.x)	x (x.x)
Pregnancies enrolled post-partum	x (x.x)	x (x.x)	x (x.x)	x (x.x)	x (x.x)	x (x.x)	x (x.x)	x (x.x)
All outcomes	x (x.x)	x (x.x)	x (x.x)	x (x.x)	x (x.x)	x (x.x)	x (x.x)	x (x.x)
Live birth without congenital anomaly	x (x.x)	x (x.x)	x (x.x)	x (x.x)	x (x.x)	x (x.x)	x (x.x)	x (x.x)
Live birth with congenital anomaly	x (x.x)	x (x.x)	x (x.x)	x (x.x)	x (x.x)	x (x.x)	x (x.x)	x (x.x)
Neonatal death without congenital anomaly	x (x.x)	x (x.x)	x (x.x)	x (x.x)	x (x.x)	x (x.x)	x (x.x)	x (x.x)
Neonatal death with congenital anomaly	x (x.x)	x (x.x)	x (x.x)	x (x.x)	x (x.x)	x (x.x)	x (x.x)	x (x.x)

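### Cheap improvement: add a prespecified, cause-restricted anomaly count beside the all-anomaly count, which pools anomalies of every cause

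*Supplement*

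**What the plan says.** The primary outcome measure is congenital anomaly (protocol 9.3.2). Section 9.7.2.4 gives the analysis in two statements: "Congenital anomalies will be summarised and descriptive statistics will be presented", and "Congenital anomalies will be defined according to ICD10-BPA codes (codes included in Appendix E: EUROCAT Subgroups of Congenital Anomalies".

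In Appendix E the row "All anomalies" takes the whole Q-chapter plus D215, D821, D1810, P350, P351 and P371. The exclusions shown for it are minor anomalies. Further down, the same list has rows for teratogenic syndromes (Q86, P350, P351, P371), "Fetal alcohol syndrome" (Q860), valproate syndrome (Q8680) and maternal infections resulting in malformations (P350, P351, P371).

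On adjudication, 9.3.2 says: "Supporting documentation will be requested to enable independent adjudication of the diagnosis, by an external expert not participating as a study investigator". Its subject is the diagnosis; assigning a cause is not mentioned. The Appendix G template divides outcomes only by presence or absence of an anomaly, for example "Live birth with congenital anomaly".

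Sections 9.7.2.5 and 9.7.2.6 plan no sensitivity or subgroup analysis. Section 9.3 collects "Age (at start of pregnancy, categorized into" bands, and also medications, comorbidities and family history of congenital disorders. None of these is tied to the anomaly summary. The stratification by other lipid-modifying therapies in 9.7.2.7 is written for the infant health and development objective.

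**The concern.** Some anomalies in the primary count have a named cause other than Repatha: an infection in the mother, alcohol or valproate. The whole-chapter entry also brings in chromosomal and single-gene conditions. That step relies on how ICD-10 is organised, because the protocol does not spell it out, but the explicitly listed rows are enough to make the point.

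Pooling does two things. It dilutes a real effect on the anomalies a drug could influence. It also lets maternal age, infection or co-medication shift the total when there is no drug effect. Few cases are expected, so one or two matter. The ENCePP checklist (Appendix B) calls this a signal-detection study, and 7.2 gives the unexposed pregnancies the role of contemporary reference data. Readers will set the columns side by side even without a formal comparison, and the checklist declares confounding not applicable.

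A further risk is procedural. With so few cases, cause will be discussed in any event, and 9.1 has the sponsor run the analyses. If cases are set aside as unrelated once exposure is known and without a prior rule, the result will be hard to credit in either direction.

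**Working it through.** **Inputs from the protocol (9.5).** Target of 300 first-trimester-exposed pregnancies; overall birth-defect incidence of 3%; at most 600 unexposed pregnancies; a 10-fold increase as the level of risk to exclude.

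**Assumption, not in the documents.** A share s of coded anomalies could not be caused by the drug. Range shown: 10% to 30%.

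**The plan's own figure.** The 300 is taken from the guideline without alpha, power or formula, so it cannot be re-derived. The 2:1 cap does reproduce (2 x 300 = 600). If all 300 pregnancies have a known outcome, 300 x 0.03 = 9 anomalies are expected. An exact 95% interval for 9/300 is 1.4% to 5.6%. Its upper limit is 5.6/3.0 = 1.9 times the reference, far below 10-fold (30%).

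**Step 1: dilution.** If the risk of drug-susceptible anomalies is multiplied by RR, the pooled ratio is s + (1 - s) x RR. For RR = 2 this is 0.10 + 0.90 x 2 = 1.90 at s = 10%, and 0.30 + 0.70 x 2 = 1.70 at s = 30%. Added cases per 300 are 9 x (1 - s).

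**Step 2: case mix with no drug effect.** If the risk of the other anomalies is multiplied by m, added cases per 300 are 9 x s x (m - 1).

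**Step 3: illustrative power.** 300 versus 600, two-sided 5%, true doubling of drug-susceptible anomalies. The plan tests nothing; this only gauges the information lost.

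| s | Non-drug cases of 9 | Restricted baseline | Doubling as seen in pooled count | Cases added by that doubling | Cases added by case mix, m = 2 | m = 3 | Power, pooled | Power, restricted |
|---|---|---|---|---|---|---|---|---|
| 10% | 0.9 | 2.70% | 1.90 | 8.1 | 0.9 | 1.8 | 50% | 53% |
| 15% | 1.35 | 2.55% | 1.85 | 7.65 | 1.35 | 2.7 | 47% | 51% |
| 20% | 1.8 | 2.40% | 1.80 | 7.2 | 1.8 | 3.6 | 43% | 49% |
| 30% | 2.7 | 2.10% | 1.70 | 6.3 | 2.7 | 5.4 | 36% | 44% |

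**Step 4: the sizes compared.** Case mix alone moves the pooled rate from 3.0% to 3.3-3.9% (m = 2) or 3.6-4.8% (m = 3). A doubling of drug-susceptible anomalies moves it to 5.1-5.7%. Chance alone has a standard deviation of sqrt(300 x 0.03 x 0.97) = 3.0 cases. Restricting the count gains about 3 to 8 points of illustrative power.

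**The case against.** Several arguments on the other side stand.

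- The all-anomaly count is the one that matches the benchmark. Section 9.5 speaks of an overall incidence of 3% and an increase in the overall incidence of malformations. A restricted count has no reference rate in the documents. The pooled count must therefore stay.
- A reader might infer that the percentage follows age and case mix rather than Repatha. The working does not support that: at equal fold change, the drug effect moves the pooled count more at every assumed share.
- A reader might infer that a trisomy would be hidden in the total. The ENCePP checklist says endpoints are reported verbatim, coded in ICD10-BPA and adjudicated. With about nine cases, each one is identifiable, and fetal alcohol syndrome, valproate syndrome and maternal infections have their own rows.
- A reader might infer that Appendix E has no chromosomal rows. The table as available is broken, ends at maternal infections and lacks its footnotes, so nothing can be concluded from what it does not show.
- Section 9.7.1.1 calls Appendix G an example for interim reports. It does not fix a single headline percentage.
- No separate analysis plan is shown, and table layout is often left to one.

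What these arguments do not supply is a rule. Being able to identify a case is not the same as deciding in advance, without knowledge of exposure, which cases form the cause-restricted count. A body-system breakdown does not produce that total either. The outcome definition and the adjudicator's remit belong in the protocol.

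**Conclusion.** The point holds as a modest, low-cost improvement. The primary outcome counts coded major anomalies whatever their cause, and the protocol prespecifies no count restricted by cause. If 10-30% of anomalies could not be drug-caused, a true doubling of the rest is seen as 1.7- to 1.9-fold, and shifts in age or case mix add noise of about 1 to 5 cases per 300. The pooled count remains responsive to a drug effect, and the 10-fold statement in 9.5 is not threatened.

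The size rests on the assumed share, on 300 exposed pregnancies with known outcome and on the 3% rate. The documents give no age distribution for either cohort, so the direction of any case-mix difference is unknown. The gain in precision is small. The stronger reason to act is that a prior rule prevents selective setting aside of cases.

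**What to change.** In 9.7.2.4:

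1. Keep the all-major-anomaly count and name it as the figure to be read against the 3% overall rate.
2. Add a second prespecified count that excludes chromosomal anomalies, monogenic syndromes and anomalies with an established other cause (P350, P351, P371, Q860, Q8680). Other Q86 codes stay in, since a teratogenic syndrome from another agent should not be removed by default.
3. Tabulate both counts by exposure column, and state that the restricted count is not compared with 3%.

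In 9.3.2, extend the external adjudicator's task to assigning the cause category, blind to Repatha exposure, from documents with exposure details removed.

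The cost is one adjudication field, redaction of the supporting documents and one set of table rows. The restricted count has slightly fewer events: about 6.3 to 8.1 expected instead of 9 under the assumed shares.

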#### Study Design Schema

Enrolment occurs at the time of identification of the pregnancy by the study site

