#### 9.7.2 Planned Method of Analysis

#### 9.7.2.1 General Considerations

Statistical analyses will be descriptive only. No statistical inference or imputations of missing data are planned.

Subject demographics and baseline characteristics will be summarised. Summary statistics for continuous variables will include the number of subjects, mean, median, standard deviation or standard error, minimum, and maximum. For categorical variables, the frequency and percentage will be reported.

Collection of study data may be both retrospective and/or prospective, depending on the time of enrolment of each study subject during the study observation period. Data obtained from retrospective and prospective subject identification will be reported separately.

Multiple pregnancies, occurring in the same woman within the study period, will be reported as separate pregnancies (with an addition of a relevant footnote in the respective tables, indicating that two or more pregnancies occurred in the same woman).

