## Appendix F. Pregnancy Outcome Definitions\*

Pregnancy outcome: the end products of pregnancy which include three main categories:

- Fetal death, termination of pregnancy and live birth.
- Fetal death (intrauterine death, in utero death): death prior to complete expulsion or extraction from its mother of a product of conception, irrespective of the duration of pregnancy; the death is indicated by the fact that after such separation the fetus does not show any evidence of life (WHO ICD 10).

Early fetal death (before 22 completed weeks of gestation) comprises ectopic pregnancy and miscarriage and late fetal death (after 22 completed weeks of gestation) is known as stillbirth.

- Ectopic pregnancy: extrauterine pregnancy, early fetal death most often in the Fallopian tube.
- Miscarriage: spontaneous abortion, molar pregnancy.
- Termination of pregnancy (induced abortion, elective abortion): artificial interruption of pregnancy.
- Live birth: the complete expulsion or extraction from its mother of a product of conception, irrespective of the duration of the pregnancy which, after such separation, breathes or shows any evidence of life. (WHO ICD 10).
- Gestational age or length: the duration of gestation is measured from the first day of the last normal menstrual period. Gestational age is expressed in completed days or completed weeks (eg, events occurring 280 to 286 days after the onset of the last menstrual period are considered to have occurred at 40 weeks of gestation).
- Last menstrual period (abbreviation LMP): according to international consensus, the gestational age is measured from the first day of the LMP.
- Birth weight: the initial weight of the infant at birth.
- Pre-term birth (previous term: premature birth): less than 37 completed weeks (less than 259 days) of gestation.

Term birth: from 37 to less than 42 completed weeks (259 to 293 days).

- Post-term birth: 42 completed weeks or more (294 days or more).
- Low birth weight: less than 2,500 gram (up to and including 2,499 g) of body weight of the newborn at birth.
- Intrauterine growth retardation (small for gestational age): the observed weight of a live born infant or size of a fetus is lower than expected on the basis of gestational age.

\*EMEA/CHMP Guideline on Exposure to Medicinal Products During Pregnancy

			1	Fiming of Rep	oatha ® expos	ure		

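### Prospective pregnancy loss is planned as a crude percentage although women enter at different gestational weeks, so it is understated and its comparability across exposure groups goes unchecked

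*Supplement*

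**What the plan says.** - **Summary measure.** Section 9.7.2.4: "Secondary objective outcome measures will be summarised and descriptive statistics will be presented". Section 9.7.2.1: "For categorical variables, the frequency and percentage will be reported". No life-table or delayed-entry method is named, and Section 9.7.2.5 plans no sensitivity analysis.
- **Entry.** Study Design Schema: "Enrolment occurs at the time of identification of the pregnancy by the study site". Section 9.2.3 sets no upper gestational limit and has no exclusion criteria.
- **Handling of entry time.** Section 9.7.2.1 notes that data collection may be retrospective or prospective, "depending on the time of enrolment of each study subject during the study observation period", and adds: "Data obtained from retrospective and prospective subject identification will be reported separately". Nothing else addresses it.
- **Display.** The Appendix G template has a pre-partum and a post-partum panel. Rows such as "Miscarriage without congenital anomaly" carry n (%) under one N per exposure column, with the unexposed column alongside. Pregnancies continuing at data cut-off are a row of the pre-partum panel.
- **Use of the unexposed group.** Section 7.2 and the Abstract describe it as contemporary reference data for reading the exposed outcomes. Section 9.7.2.4 rules out a formal comparison.
- **Definitions.** Section 9.3 lists miscarriage, "Spontaneous abortion" and molar pregnancy separately and refers to Appendix F, which has: "Miscarriage: spontaneous abortion, molar pregnancy". Appendix F divides miscarriage from stillbirth at 22 completed weeks.

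**The concern.** A woman enrolled during pregnancy must still be pregnant when the site identifies her, so she can contribute a loss only from her entry week onward. A woman entering at week 6 and one entering at week 20 share a denominator in the pre-partum panel, yet most of the miscarriage risk is already past for the second. The crude percentage mixes these and falls as entry gets later.

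Describing pregnancy outcomes in exposed and in unexposed women is a secondary objective in its own right (Section 8.2), so an understated percentage matters even without a comparison. Readers will also set the columns beside each other, since that is why the unexposed cohort is enrolled. If entry week differs by group, the difference in loss can be an artefact of timing, in either direction. The plan provides nothing from which a reader could tell.

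**Working it through.** **The plan's own figures.** The documents state no loss rate and no precision target for loss. The one cohort figure, 600 unexposed pregnancies, reproduces as 2 × 300 and has no bearing here. All loss rates, hazard shapes and entry weeks below are assumptions.

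**Step 1. Formula.** Let h(t) be the weekly hazard of spontaneous loss for weeks t = 5 to 21, that is, before 22 completed weeks. For a woman entering at week e, the loss that can be observed is

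risk(e) = 1 − product over t = e to 21 of [1 − h(t)].

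**Step 2. Exponentially falling hazard.** Take h(t) = c × exp(−k × (t − 5)), with c solved so that risk(5) = 15%. There is no exposure effect.

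| Decay k | c | Entry week 8 | Entry week 12 | Ratio |
|---|---|---|---|---|
| 0.10 | 0.0188 | 10.5% | 6.0% | 1.7 |
| 0.25 | 0.0361 | 7.2% | 2.6% | 2.8 |
| 0.50 | 0.0627 | 3.5% | 0.5% | 7.3 |

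With k = 0.25, weeks 8 and 12 give 4.8% and 1.7% if total loss is 10%, and 9.8% and 3.5% if it is 20%.

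**Step 3. A different shape, checkable by hand.** Put 50% of losses evenly in weeks 5–8, 35% in weeks 9–12 and 15% in weeks 13–21, with total loss 15%.
- Entry at week 8: losses still to come are 0.15 × (0.125 + 0.35 + 0.15) = 0.0938. Pregnancies still at risk are 1 − 0.15 × 0.375 = 0.9438. Crude loss is 0.0938 / 0.9438 = 9.9%.
- Entry at week 12: 0.15 × (0.0875 + 0.15) = 0.0356, divided by 1 − 0.15 × 0.7625 = 0.8856, gives 4.0%.
- The same formula gives 13.4% at week 6, 6.8% at week 10, 1.7% at week 16 and 0.6% at week 20.

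**Step 4. Mixed entry, no exposure effect.**
- Early mix (50% at week 6, 30% at week 8, 20% at week 10): 0.5 × 13.4 + 0.3 × 9.9 + 0.2 × 6.8 = 11.0%.
- Late mix (20% at week 8, 40% at week 12, 20% at week 16, 20% at week 20): 0.2 × 9.93 + 0.4 × 4.02 + 0.2 × 1.73 + 0.2 × 0.58 = 4.1%.
- The ratio is 2.7 from timing alone.
- In the other direction, a true hazard ratio of 1.5 in late-entering exposed women, set against early-entering unexposed women, shows as 0.54.
- With the late mix in both groups, the same hazard ratio gives a crude ratio of 1.48, against 1.45 for loss from week 5. The contrast survives, but both percentages are too low.

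**Step 5. Does delayed entry recover the truth?** This used 400 simulated cohorts under the Step 3 hazard, where true loss from week 6 is 13.4%.

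| Cohort | Crude | Delayed-entry Kaplan-Meier | SD of estimate |
|---|---|---|---|
| n = 300, early mix | 11.1% | 13.5% | 2.4 points |
| n = 600, late mix with 10% entering at week 6 | 5.4% | 13.6% | 3.0 points |

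The larger cohort has the wider spread because few of its women are at risk in the early weeks.

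**The case against.** **The analysis is descriptive and no formal comparison is planned.** True, and this limits the harm. It does not remove it, because the understatement exists within each group and the unexposed figures are offered as reference data.

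**Estimator detail may be left to an analysis plan.** None is shown. But the protocol does not leave the measure open: it names frequency and percentage. Appendix G is an example template for interim reports and does not define its N, so division by all enrolled pregnancies is a natural reading of it, not a stated rule.

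**Losses before enrolment are not wholly invisible.** They can enter retrospectively (Section 9.2.3.1). Sites are asked to enrol regardless of known outcome and to log pregnant FH women each year (Section 9.9.2). This helps to assess ascertainment, but retrospective data are reported separately and do not correct the prospective panel.

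**A reader might infer that the exposed/unexposed contrast is biased, or that a false excess with exposure is to be expected.** The documents do not support that. They give no distribution of entry week. Section 9.2.2 describes an additional route, sponsor surveillance, for exposed pregnancies, but not when in gestation such reports arrive. Late reports would push the contrast the other way.

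**A reader might infer that spontaneous abortions would be lost for want of a row in Appendix G.** They would not. Section 9.3 sends the reader to Appendix F, which places them under miscarriage. What remains is untidy wording: molar pregnancy falls under miscarriage in Appendix F but has its own row in Appendix G, and Section 9.3.2 speaks of spontaneous loss.

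**The data may not be there.** Section 9.3 lists gestational age only under infant status at delivery, and the notification worksheet with a termination date is for exposed women only (Section 11, Appendix I). This stands in part. The 22-week boundary in Appendix F already requires sites to know gestational age at loss, but the protocol should say that it is recorded.

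**Conclusion.** The concern holds for the prospective panel. Followed as written, the plan understates pregnancy loss in each group, relative to loss from a common early week, by an amount set by entry week. The exposed and unexposed percentages can be read together only if entry week is similarly distributed, and the plan does not examine this. The prospective/retrospective split does not address it.

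The mechanism follows from the enrolment rule. The size does not: at an assumed 15% total loss, 3.5–10.5% for entry at week 8 and 0.5–6.0% at week 12 are illustrations over a range of hazard shapes, not estimates for this study. The documents settle neither the existence nor the direction of a distorted group contrast. This is a weakness in a secondary outcome that should be mended. The terminology point is editorial only.

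**What to change.** 1. In Section 9.7.2.4, for prospectively enrolled pregnancies, add a descriptive cumulative incidence of spontaneous loss to 22 completed weeks. Use delayed entry at the gestational week of enrolment, treat elective termination as a competing event, and censor ongoing pregnancies.
2. Tabulate gestational week at enrolment by exposure group next to it.
3. State in Section 9.3 that the date or gestational age of loss is recorded for exposed and unexposed women alike.
4. Add a note that the columns for second- or third-trimester exposure and for exposure throughout pregnancy are not comparable loss rates. A pregnancy must survive to reach them, and delayed entry alone does not correct that.
5. As an editorial matter, use one set of terms for miscarriage, spontaneous abortion and molar pregnancy in Sections 9.3 and 9.3.2 and Appendices F and G.

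**Cost.** Little extra analysis: last menstrual period is collected, enrolment is a defined, dated event, and the estimate stays descriptive. One date field must be confirmed in the eCRF, or added if absent. The estimate will be imprecise in the early weeks, when few women are at risk.
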